8.1.2 Safety Set

The **Safety Set** for Part A is defined as all subjects who have received at least 1 dose of study drug in Part A of Study 115. The Safety Set will be used for subject demographics and baseline characteristics and for all safety analyses unless otherwise specified.

8.2 Analysis Sets for Part B

8.2.1 All Subjects Set

The **All Subjects Set** for Part B is defined as all subjects who were enrolled (defined as subject having data in the clinical database) in Part B of Study 115. This analysis set will be used for individual subject data listings and the disposition summary table, unless otherwise specified.

8.2.2 Safety Set

The **Safety Set** for Part B is defined as all subjects who have received at least 1 dose of study drug in Part B of Study 115. The Safety Set will be used for subject demographics and baseline characteristics and for all safety analyses unless otherwise specified.

9 STATISTICAL ANALYSIS

The analyses will be performed separately for Part A and Part B, unless otherwise specified.

9.1 Statistical Analysis for Part A

9.1.1 General Considerations

The safety analyses for Part A will be presented for overall with all the subjects pooled together, unless otherwise specified.

The precision standards for reporting safety variables are provided in an internal Biometrics document that specifies the programming rules including the precision for derived variables.

Continuous variables will be summarized using the following descriptive summary statistics: the number of subjects (n), mean, SD, SE, median, minimum value (min), and maximum value (max).

Categorical variables will be summarized using counts and percentages.

Baseline value, unless otherwise specified, for the safety analysis will be the most recent non-missing measurement (scheduled or unscheduled) collected before the first dose of ELX/TEZ/IVA either in a parent study or in Part A of Study 115, as applicable. For assessments collected in duplicate or triplicate, the baseline value will be defined as the average of non-missing values.

Change (absolute change) from baseline will be calculated as Post-baseline value – Baseline value.

Treatment-emergent (TE) Period for Part A will include the time period starting from the date of the first dose of study drug in Part A of this open-label study to 28 days after the last dose of the study drug, or to the completion date of study participation (as defined in Section 9.1.5 of study protocol), whichever occurs first.

9.1.2 Background Characteristics

9.1.2.1 Subject Disposition

Subject disposition will be summarized for the All Subjects Set. The number and percentage of subjects in the following categories for Part A will be summarized as appropriate:

- All Subjects Set

- Safety Set
- Completed Treatment in Part A
- Prematurely discontinued treatment in Part A and the reasons for discontinuation
- Completed study in Part A
- Prematurely discontinued in Part A and the reasons for discontinuation

A listing will be provided for subjects who discontinued treatment in Part A or who discontinued study in Part A with reasons for discontinuation.

9.1.2.2 Demographics and Baseline Characteristics

Demographics and baseline characteristics will be summarized by descriptive summary statistics for the Safety Set. Demographic data will include the following:

- Age at parent study baseline (in years)
- Sex (female and male)
- Ethnicity (Hispanic or Latino, not Hispanic or Latino, and not collected per local regulations)
- Race (White, Black or African American, Asian, American Indian or Alaska Native, Native Hawaiian or Other Pacific Islander, Not Collected per Local Regulations and Other)
- Country

Parent study baseline characteristics will include the following:

- Weight (kg)
- Height (cm)
- BMI (kg/m²)

Stratification categories (in addition to sex, if applicable) used in the parent study will include the following:

- Age at Screening Visit of parent study (<18, ≥18 years)
- ppFEV₁ at Day -14 of parent study (<70, ≥70)
- CFTR modulator use at the Screening Visit of parent study (Yes, No)

Note that the parent study (study 109) had a 4-week TEZ/IVA run-in period during which the ppFEV₁ used in stratification was determined.

Disease characteristics based on parent study baseline will include the following:

- ppFEV₁ at parent study baseline (<40, ≥ 40 to <70, ≥70 to ≤90, and >90)
- ppFEV₁ at parent study baseline (continuous)
- Prior use of dornase alfa (Yes, No)
- Prior use of azithromycin (Yes, No)
- Prior use of inhaled antibiotic (Yes, No)

- Prior use of any bronchodilator (Yes, No)
- Prior use of any inhaled bronchodilator (Yes, No)
- Prior use of any inhaled hypertonic saline (Yes, No)
- Prior use of any inhaled corticosteroids (Yes, No)
- Infection with *Pseudomonas aeruginosa* within 2 years prior to screening visit (Positive, Negative) of parent study

Prior medication use definition is same as that for the baseline characteristics summary presented in the parent studies.

9.1.2.3 Medical History

Medical history (referenced to the start of parent study) will be coded by using the Medical Dictionary for Regulatory Activities (MedDRA). Medical history will be summarized descriptively by System Organ Class (SOC) and Preferred Term (PT) based on the Safety Set. The corresponding data listing will also be provided.

9.1.2.4 Prior and Concomitant Medications

Medications will be coded using the World Health Organization-Drug Dictionary and categorized as follows:

- **Prior medication:** any medication that was administered within the 56 days before the first dose of study drug in Part A in this open-label study.
- **Concomitant medication:** medication continued or newly received during the TE Period for Part A in this open-label study.
- **Post-treatment medication:** medication continued or newly received after the TE Period for Part A in this open-label study.

A given medication may be classified as a prior medication, a concomitant medication, or a post-treatment medication; both prior and concomitant; both concomitant and post-treatment; or prior, concomitant, and post-treatment.

If a medication has a missing or partially missing start/end date or time and if it cannot be determined whether it was taken before initial dosing, concomitantly during the TE Period, or beyond the TE Period, it will be considered in all 3 categories of prior, concomitant, and post-treatment medication. Details for imputing missing or partial start and/or stop dates of medication are described in [Section 12.2](#).

Prior medications and concomitant medications will be summarized descriptively by Preferred Name based on the Safety Set by 1) preferred name (PN); and 2) anatomic class (ATC) level 1, ATC level 2, and PN. Post-treatment medications will be provided separately in an individual subject data listing.

9.1.2.5 Study Drug Exposure

Study drug exposure will be summarized based on the Safety Set.

Duration of study drug exposure (in days) will be calculated as [last dose date – first dose date + 1 day] within the TE period for Part A, regardless of any interruption in dosing between the first and the last dose.

Study drug exposure (in weeks) will be summarized descriptively by the number of subjects (n), mean, SD, median, min, and max. It will also be summarized by interval, using counts and percentages.

9.1.2.6 Study Drug Compliance

Study drug compliance will be summarized based on the Safety Set and will be calculated as: $100 \times [1 - (\text{total number of days of study drug interruption in Part A of this open-label study}) / (\text{duration of study drug exposure in days in Part A this open-label study})]$. A study drug interruption on a given day is defined as an interruption of any study drug on that day.

Percentage of study drug compliance will be summarized based on Safety Set. Percentage of study drug compliance will be summarized descriptively by the number of subjects (n), mean, SD, median, min, and max. It will also be summarized in categories: <80% and \geq 80% using frequency tables.

9.1.2.7 Important Protocol Deviation

An important protocol deviation (IPD) is a deviation that may significantly affect the completeness, accuracy, or reliability of the study data or that may significantly affect a subject's rights, safety, or well-being. A protocol deviation review team will categorize IPDs according to the Protocol Deviation Plan during the study. IPD rules will be developed and finalized before database lock.

IPDs (from the clinical database or from the site deviation log) during Part A of this open-label study will be summarized descriptively based on the Safety Set. Additionally, IPDs will be provided in an individual subject data listing.

9.1.3 Safety Analysis

The primary objective of this study is the evaluation of safety and tolerability of ELX/TEZ/IVA. All safety analyses will be based on the TE Period for Part A for subjects in the Safety Set.

The overall long-term safety profile of study drug will be assessed in terms of the following safety and tolerability endpoints:

- Treatment-emergent adverse events (TEAEs)
- Clinical laboratory values
- ECGs
- Vital signs
- Pulse oximetry

Only descriptive analysis of safety will be performed and no statistical testing will be performed.

9.1.3.1 Adverse Events

AEs will be classified as pretreatment AEs, TEAEs, or post-treatment AEs, defined as follows:

- **Pre-treatment AE:** any AE occurred before the first dose date of study drug in the TE Period for Part A.
- **TEAE:** any AE that worsened (either in severity or seriousness) or newly developed at or after the first dose date of ELX/TEZ/IVA in the TE Period for Part A in this open-label study.
- **Post-treatment AE:** any AE that worsened (either in severity or seriousness) or newly developed after the TE Period for Part A.

For AEs with missing or partial start dates, if there is no clear evidence that the AEs started before or after study drug treatment start date in this OLS, then the AEs will be classified as TEAEs.

Details for imputing missing or partial start dates of adverse events are described in [Section 12.3](#).

An overview of all TEAEs during TE period will be summarized and include the following categories:

- Number of TEAEs (total number of TEAEs only)
- Subjects with any TEAEs
- Subjects with TEAEs by strongest relationship
- Subjects with TEAEs by maximum severity
- Subjects with TEAEs leading to study drug discontinuation
- Subjects with TEAEs leading to study drug interruption
- Subjects with Grade 3/4 TEAEs
- Subjects with related TEAEs
- Subjects with serious TEAEs
- Subjects with related serious TEAEs
- Subjects with TEAE leading to death

The frequency counts and percentages as well as the exposure adjusted event rate will be presented for the above overview table. The exposure adjusted rate will not be presented for strongest relationship and maximum severity categories.

The following summary tables of TEAEs will be presented for overall:

- All TEAEs
- TEAEs by strongest relationship
- TEAEs by maximum severity
- Related TEAEs
- Grade 3/4 TEAEs
- Serious TEAEs

- Related serious TEAEs
- TEAEs leading to treatment discontinuation
- TEAEs leading to treatment interruption
- TEAEs leading to death

Summaries will be presented by MedDRA SOC and PT using frequency counts and percentages (i.e., number and percentage of subjects with an event) and the exposure adjusted event rate (except for summary by strongest relationship and maximum severity). When summarizing the number and percentages of subjects, subjects with multiple occurrences of the same adverse event will be counted once, and only the maximum severity level will be presented in the severity summaries, and the strongest relationship level in the relationship summaries. Missing severity levels will not be included in the Grade 3/4 TEAE summaries; missing relationship will be considered as related and included in the related TEAE and related serious TEAE summaries.

Additional summary table will be presented for TEAEs overall in number and percentage of subjects.

- All TEAEs by PT

All AEs, including pre-treatment AEs, TEAEs, and post-treatment AEs, will be presented in an individual subject data listing based on the All Subjects Set. In addition, separate listings containing individual subject adverse event data for TEAEs leading to treatment discontinuation, TEAEs leading to treatment interruption, Grade 3/4 TEAEs, SAEs and AEs leading to death will be provided, with a flag indicating the TEAE status for SAEs and deaths.

9.1.3.2 Clinical Laboratory Assessments

For the laboratory assessments during TE period for Part A, the observed values and change from baseline values of the continuous hematology, coagulation and chemistry results will be summarized in SI units at each visit.

The number and percentage of subjects meeting at least 1 threshold analysis criterion event during the TE period for Part A will be summarized. The threshold analysis criterion shift from baseline will also be summarized for selected laboratory parameters. The threshold analysis criteria are provided in [Section 12.4](#).

Results of positive urine/serum pregnancy test will be presented in individual subject data listings only. For positive serum pregnancy listing, subjects with serum HCG which are abnormally high will be selected.

In addition, a listing containing individual subject hematology, chemistry, and coagulation values will be provided. This listing will include data from both scheduled and unscheduled visits.

9.1.3.3 Electrocardiogram

For the following ECG interval measurements during the TE period for Part A, a summary of observed values and change from baseline values will be provided at each visit (in msec): RR, PR, QT, and QT corrected for HR (QTcF), QRS duration, and HR (beats per minute).

The number and percentage of subjects meeting at least 1 threshold analysis criterion event during the TE period for Part A will be summarized. The threshold analysis criteria are provided in [Section 12.4](#).

9.1.3.4 Vital Signs

For the vital signs measurements during the TE period for Part A, the observed values and change from baseline values will be summarized at each visit. The following vital signs parameters will be summarized: BMI (kg/m²), weight (kg), systolic and diastolic blood pressure (mm Hg), body temperature (°C), pulse rate (beats per minute), and respiratory rate (breaths per minute).

The number and percentage of subjects meeting at least 1 threshold analysis criterion event during the TE period for Part A will be summarized. The threshold analysis criteria are provided in Section 12.4.

9.1.3.5 Pulse Oximetry

For the percent of oxygen saturation measurements using pulse oximetry during the TE period for Part A, a summary of observed values and change from baseline values will be provided at each visit.

The number and percentage of subjects with shift changes from baseline (normal/missing and low according to the reference range) to the lowest percent of oxygen saturation during the TE period for Part A will be summarized.

9.1.3.6 Physical Examination

No tables/figures/listings will be provided for physical examination data.

9.1.3.7 Ophthalmology Examination

Ophthalmology examination results will be provided in a data listing.

9.1.3.8 COVID-19 Impacted Visits

A listing containing subjects' visits impacted due to COVID-19 will be provided.

9.1.3.9 Safety Supportive Analysis

9.1.3.10 Adverse Events of Special Interest

For this study, elevated transaminases events and rash events, as determined by MedDRA Preferred Terms in the respective Customized MedDRA Queries (CMQ), are considered as adverse events of special interest. The corresponding AE data will be summarized in terms of frequency counts and exposure adjusted rates.

For treatment-emergent elevated transaminases events and rash events, the following categories will be summarized:

- Subjects with events
- Subjects with events by maximum severity
- Subjects with events leading to treatment discontinuation
- Subjects with events leading to treatment interruption
- Subjects with serious events
- Subjects with related serious events

- Subjects with events leading to death
- Duration of events
- Time-to-onset of first event (with the first dose date of ELX/TEZ/IVA in the open-label study Part A as the reference while calculating time-to-onset)

Note that for maximum severity, duration of events and time to onset of first event, the exposure adjusted rates will not be presented.

In addition, for treatment-emergent rash events, the above categories will be summarized for the following subgroups:

- Sex (male, female)
- Female subjects with concomitant hormonal therapy (Yes, No)

9.2 Statistical Analysis for Part B

9.2.1 General Considerations

The safety analyses for Part B, unless otherwise specified, will be similar to the safety analyses for Part A. For subjects who depart this study to enroll in another qualified Vertex study and return to this study, details of the associated analysis will be specified in this Section.

In the unlikely scenario that only a few patients roll over into Part B, a descriptive summary may not be performed.

Baseline value, unless otherwise specified, for the safety analysis will be the most recent non-missing measurement (scheduled or unscheduled) collected before the first dose of ELX/TEZ/IVA either in a parent study or in Part A of Study 115, whichever is earlier. For assessments collected in duplicate or triplicate, the baseline value will be defined as the average of non-missing values.

Treatment-emergent (TE) Period for Part B will include the time period starting from the date of the first dose of study drug in Part B of this open-label study to 28 days after the last dose of the study drug, or to the completion date of study participation (as defined in Section 9.1.5 of study protocol), whichever occurs first. For subjects who enroll in another qualified Vertex study before completing this study and resume participation in this study, the TE Period will exclude the time spent in the other study.

Prior and Concomitant Medications

For Part B, medications will be categorized as:

- **Prior medication:** any medication that was administered within the 56 days before the first dose of study drug in Part B of Study 115. For subjects who enroll in another qualified Vertex study and resume participation in this study, any new or changed medication administered after the Departing Visit and prior to the first dose of study drug after resuming participation in this study will also be considered prior medication.
- **Concomitant medication:** medication continued or newly received at, or after, initial dosing of study drug through the end of 115 Part B TE Period.

- **Post-treatment medication:** medication continued or newly received after 115 Part B TE Period.

Study Drug Exposure

Study drug exposure will be summarized based on the Safety Set for Part B. Duration of study drug exposure (in days) will be calculated as [last dose date – first dose date + 1 day] within the TE period for Part B, regardless of any interruption in dosing between the first and the last dose. For subjects who enroll in another qualified Vertex study and resume participation in this study, time spent in the other study will be excluded.

Study Drug Compliance

Study drug compliance will be summarized based on the Safety Set and will be calculated as: $100 \times [1 - (\text{total number of days of study drug interruption in Part B of this open-label study}) / (\text{duration of study drug exposure in days in Part B this open-label study})]$. A study drug interruption on a given day is defined as an interruption of any study drug on that day. For subjects who enroll in another qualified Vertex study and resume participation in this study, time spent in the other study will be excluded.

9.2.2 Background Characteristics

The same set of analyses as Part A will be performed for Part B based on Part B's analysis sets and the definitions in the General Consideration Section 9.2.1.

9.2.3 Safety Analysis

AEs in Part B are defined as follows:

- **Pretreatment AE:** any AE that occurred before the first dose date of study drug in the TE Period for Part B. For subjects who depart this study to enroll in another qualified Vertex study before completing this study and return to this study, pretreatment AEs also include any AE that occurred after participating in the other qualified Vertex study and before the first dose of study drug after resuming participation in Study 115 Part B.
- **TEAE:** any AE that worsened (either in severity or seriousness) or newly developed at or after the first dose date of ELX/TEZ/IVA in the TE Period for Part B in this open-label study.
- **Post-treatment AE:** any AE that worsened (either in severity or seriousness) or newly developed after the TE Period for Part B.

The same set of safety analyses as Part A will be performed for Part B based on Part B's Safety Set and its treatment emergent period when applicable.

10 Interim and DMC Analyses

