Urinalysis	X			X	X	X	
Hematology	X	X		X	X	X	
Coagulation	X	Week 48		X	X	X	
Serum chemistry	X	X		X	X	X	
Study drug count	X	X		X	X		

Table 3-2 Study VX19-445-115: Part B Treatment Period and Safety Follow-up Visit							
Event/Assessmenta	Treatment Period Part B				Part B ETT Visit/ Departing Visitb	Part B Safety Follow-up Visit (28 ± 7 Days After Last Dose)c	Comments
	Day 1/ Returning Visitd	Weeks 12, 24, 36, 48, 60, 72, 84 (± 5 Days)	Weeks 4, 8, 16, 20, 28, 32, 40, 44, 52, 56, 64, 68, 76, 80, 88, 92 (± 5 Days)	Week 96 (± 5 Days)			
Study drug dosing	Day 1 through evening before Part B Week 96 Visit						Subjects on study drug interruption from Part A or another qualified Vertex study may NOT begin dosing in Part B until they meet the resumption criteria in Section 9.8. The first dose of Part B will be given at the Day 1 Visit. Refer to Section 9.6.1 for study drug administration details.
Medications review	Continuous from signing of the Part B ICF through completion of study participation						Completion of study participation is defined in Section 9.1.5.
Treatments and procedures review	Continuous from signing of the Part B ICF through completion of study participation						
AEs and SAEs	Continuous from signing of the Part B ICF through completion of study participation						

AE: adverse event; ETT: early termination of treatment; ICF: informed consent form; PE: physical examination; SAE: serious adverse event

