4 INTRODUCTION

This statistical analysis plan (SAP) documents the planned final analyses of VX19-445-115 (Study 115) which is based on an approved clinical study protocol (CSP) (Version 2.2, dated 21 December 2021), as well as the most recent approved electronic case report form (eCRF), and the most recent approved eCRF completion guidelines.

The Vertex Biometrics Department will perform the statistical analysis described in this document; SAS (Version 9.4 or higher) will be used to generate all statistical outputs (tables, figures, listings, and datasets). The SAP (Methods) will be finalized and approved prior to database lock of Study 115 Part A. Any revisions to the approved SAP will be documented and approved in an amendment to the SAP.

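### An AE carried into Part B without worsening that then leads to discontinuation or interruption in Part B is left out of the Part B tables of those events

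*SAP*

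**What the plan says.** SAP section 9 analyses Parts A and B separately unless otherwise specified. It specifies no pooled table of AEs across the two Parts.

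For Part B, SAP 9.2.1 starts the treatment-emergent (TE) period at the first Part B dose: "the time period starting from the date of the first dose of study drug in Part B of this open-label study". SAP 9.2.3 then sorts AEs against that date:

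- Pretreatment: "any AE that occurred before the first dose date of study drug in the TE Period for Part B".
- TEAE: one whose severity or seriousness has increased, or that "newly developed at or after the first dose date of ELX/TEZ/IVA in the TE Period for Part B".

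The outputs are inherited from Part A: "The same set of safety analyses as Part A will be performed for Part B", on the Part B Safety Set and TE period. They include the overview row "Subjects with TEAEs leading to study drug discontinuation", its interruption counterpart, and the SOC/PT tables of both (SAP 9.1.3.1). The separate listings of discontinuations and interruptions are also limited to TEAEs. The listings of SAEs and of AEs leading to death are not: they carry a flag for TEAE status instead. The AESI rows for discontinuation and interruption (SAP 9.1.3.10) count treatment-emergent events.

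Two outputs are not tied to AE onset. One is the all-AE listing, which includes pretreatment AEs. The other is the disposition summary and listing, which give reasons for stopping treatment (SAP 9.1.2.1, applied to Part B by 9.2.2).

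**The concern.** The boundary between the Parts is administrative. Drug and dose are the same, and Protocol 9.1.1 makes the Part A Week 48 Visit the start of Part B treatment for those who continue. A subject can therefore cross it with an AE under way while on study drug. Protocol 8.1 also admits subjects who had interruptions in Part A, and Protocol Table 3-2 provides for subjects still on interruption: "Subjects on study drug interruption from Part A or another qualified Vertex study may NOT begin dosing in Part B" until resumption criteria are met.

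A rule based on onset or worsening suits a table of new events. It fits poorly when the question is whether an AE led to stopping or interrupting the drug in Part B, because that depends on when the action happened. Safety and tolerability is the study's only objective and the analysis is purely descriptive, so these counts are the result itself. A short count of AE-related drug actions would flatter tolerability in the longer Part.

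**Working it through.** **1. Classify each case under SAP 9.2.3.** The drug action falls in Part B throughout, in a subject dosed in Part B.

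| AE onset | Worsened in severity or seriousness in Part B? | Part B class | In the Part B discontinuation/interruption tables? |
|---|---|---|---|
| On or after first Part B dose | not relevant | TEAE | Yes |
| Before first Part B dose | Yes | TEAE | Yes |
| Before first Part B dose | No | Pretreatment | No |

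Only the third row is a gap.

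**2. Can the third row occur?** Yes, on the protocol's own terms. One liver interruption criterion in Protocol 9.8.1 is met by duration: a transaminase elevation above 5 × ULN lasting more than 2 weeks. The liver discontinuation criterion can apply even when levels have since improved. An elevation that spans the boundary can therefore meet either criterion in Part B with no rise in recorded severity. Elevated transaminases are also an AESI, so the AESI rows share the gap.

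**3. Where would the event still be seen?**

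| Output for Part B | Withdrawal | Interruption |
|---|---|---|
| TEAE table and dedicated listing | No | No |
| AESI row, if the term qualifies | No | No |
| Disposition with reasons | Yes | No counterpart |
| Compliance | Not applicable | Days only, not linked to an AE |
| All-AE listing | Yes | Yes |

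**4. Does the Part A table pick it up?** The AE keeps its Part A TEAE status if it arose or worsened in the Part A TE period. Action taken is a classification held on each AE record, and the AE data items in Protocol 13.1.1.3 include no date for the action. Whether Part A output shows the action therefore depends on when the record is updated, and the documents do not describe this.

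**5. Size.** The plan gives no figure for this point. Its only relevant number is the expected enrolment of up to about 158 (SAP 7.2), which is an upper bound for Part B. With N subjects dosed in Part B, k omitted subjects lower the Part B percentage by 100 × k / N points. N below 158 is assumed.

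| N dosed in Part B | k = 1 | k = 3 |
|---|---|---|
| 158 (maximum) | 100/158 = 0.63 | 300/158 = 1.90 |
| 120 | 100/120 = 0.83 | 300/120 = 2.50 |
| 80 | 100/80 = 1.25 | 300/80 = 3.75 |
| 50 | 100/50 = 2.00 | 300/50 = 6.00 |

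The documents give no basis for k, and k = 0 is possible. Purely as illustration, if three subjects withdrew for AEs in Part B and one was in the third row, the AE table would show two of three, a 33% under-count.

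**The case against.** **Worsened AEs are captured.** A reader who sees only the new-onset limb might infer that every AE starting in Part A and causing withdrawal in Part B is lost. The definition also has a worsening limb, so that reading fails. Nor does the SAP contain a rule attributing drug actions to the Part of onset; the gap is a consequence of the TEAE definition.

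**The event is visible elsewhere.** This stands for withdrawals, through disposition and the all-AE listing. For interruptions only the all-AE listing remains.

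**Entry rules shrink the exposed group.** Part B excludes subjects who permanently discontinued in Part A and those whose drug intolerance the investigator judges a risk. After an interruption longer than 72 hours the subject should be clinically stable before resuming. A recurrence after recovery would plausibly be a new or worsened AE and so a Part B TEAE. This makes the case uncommon. It does not exclude an ongoing AE that later leads to action at unchanged severity.

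**Limiting AE tables to TEAEs is protocol-specified (Protocol 12.3.4.1).** True, and the TEAE tables should stay. The SAP already looks beyond TEAEs where it matters, by listing SAEs and AEs leading to death with a TEAE flag. Extending that to drug actions is a small step.

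**The size is assumed.** Agreed. The SAP also says a Part B summary may not be produced if only a few subjects roll over.

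**Conclusion.** The gap is real and narrow. An AE with onset before the first Part B dose, not worsening in severity or seriousness in Part B, that leads to discontinuation or interruption during Part B is omitted from the Part B TEAE tables and listings of those actions and from the matching AESI rows. The Part B AE-discontinuation count can therefore be lower than the disposition count, with no reconciliation planned; for interruptions there is no second count to compare. Each omitted subject is 0.6 points at the maximum N of 158 and 2.0 at an assumed 50. How many there will be cannot be derived.

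A reader might also infer that such a withdrawal disappears from both Parts once Part A is locked. The documents do not support that as a finding. The SAP refers to the lock only to date its own approval, "prior to database lock of Study 115 Part A", and does not say how later updates to an AE spanning both Parts are handled.

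The conclusion rests on reading the definitions as written. It also assumes that disposition has a reason category for adverse events, since the documents do not list the categories. The point merits a change because the rule can under-count a tolerability result in a study whose output is descriptive safety counts, and the repair is cheap.

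**What to change.** In SAP 9.2.3:

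1. Keep the TEAE tables unchanged. Beneath the Part B discontinuation and interruption counts, and in the matching AESI rows, add a separate footnoted row for AEs with onset before the first Part B dose, not worsened in Part B, that led to that action during Part B. Flag these AEs in the discontinuation and interruption listings.
2. Assign an AE to this row by the date of the drug action, taken from dosing and disposition dates, since the AE data items carry no action date.
3. Reconcile at subject level: subjects with a TEAE leading to discontinuation, plus subjects only in the new row, plus subjects enrolled in Part B but never dosed there who stopped for an AE, should equal the Part B disposition count for adverse events. Explain any difference.
4. Report the never-dosed subjects through Part B disposition and a listing. They are in the Part B All Subjects Set but not its Safety Set. Placing them in the Part A table would show a discontinuation there for subjects who had not permanently discontinued in Part A.

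The cost is a paragraph of SAP text, one extra row per affected table, and programming to link AE records to dosing records. No new data, visits or procedures are needed. The downside is that the row is not strictly treatment-emergent, hence the footnote.
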